8. INTERIM ANALYSIS

After the last subject in the primary Study OHB-607-202 has completed the last study visit, an interim analysis for Study SHP607-203 was to be performed for all enrolled subjects who had either completed the 24 months CA visit assessments or prematurely withdrawn from Study SHP607-203, and after all associated data would have been entered into the database with queries and discrepancies resolved.

Since study SHP607-203 will be terminated early before the last subject in the primary Study OHB-607-202 has completed the last study visit, the planned interim analysis will not be conducted.

9. DATA HANDLING CONVENTIONS

9.1 General Data Reporting Conventions

Continuous variables will be summarized using the following descriptive statistics: n, mean, median, standard deviation, quartile 1 (Q1), quartile 3 (Q3), minimum and maximum.

Categorical and count variables will be summarized by the number of subjects (n) and the percent of subjects in each category. The denominator for the proportion will be based on the total number of subjects for each treatment group and overall within the analysis set of interest.

Unless specified otherwise, median, mean, Q1 and Q3 will use 1 decimal place beyond the precision of data used for the measurement; standard deviation of the mean will use 2 decimal places beyond the precision; minimum and maximum values will use the same number of decimal places as the precision.

9.2 Handling of Missing, Unused, and Spurious Data

9.2.1 Missing Date Information for Adverse Events

To facilitate categorization of AEs as related to study procedure, imputation of start dates can be used. For AEs, the default is to only impute incomplete (i.e., partially missing) start dates. Incomplete stop dates may also be imputed when calculation of the duration of an AE is required. If imputation of an incomplete stop date is required, and both the start date and the stop date are incomplete for a subject, impute the start date first.

9.2.1.1 Incomplete Start Date

If the stop date is complete and the imputed start date is after the stop date, then the start date will be imputed using the stop date.

Missing day and month

- If the year of the incomplete start date is the same as the year of the date of informed consent, then the day and month of the date of informed consent will be assigned to the missing fields.
- If the year of the incomplete start date is before the year of the date informed consent, then December 31 will be assigned to the missing fields.
- If the year of the incomplete start date is after the year of the date of informed consent, then January 01 will be assigned to the missing fields.

Missing Month only

The day will be treated as missing and both month and day will be replaced according to the above procedure.

Missing Day only

- If the month and year of the incomplete start date are the same as the month and year of the date of informed consent, then the day of the date of informed consent will be assigned to the missing day.
- If either the year is before the year of the date of informed consent or if both years are the same but the month is before the month of the date of informed consent, then the last day of the month will be assigned to the missing day.
- If either the year is after the year of the date of informed consent or if both years are the same but the month is after the month of the date of informed consent, then the first day of the month will be assigned to the missing day.

9.2.1.2 Incomplete Stop Date

If the imputed stop date is before the start date (imputed or non-imputed start date), then the imputed stop date will be equal to the start date.

Missing Day and Month

- If the year of the incomplete stop date is the same as the year as of the end of study date, then the day and month of the end of study date will be assigned to the missing fields.
- If the year of the incomplete stop date is before the year of the end of study date, then 31 December will be assigned to the missing fields.
- If the year of the incomplete stop date is after the year of the end of study date, then the stop date will be imputed as the end of study date.

Missing Month only

- The day will be treated as missing and both month and day will be replaced according to the above procedure.

Missing Day only

- If the month and year of the incomplete stop date are the same as the month and year of the end of study date, then the day of the end of study date will be assigned to the missing day
- If either the year is before the year of the end of study date or if both years are the same but the month is before the end of study date, then the last day of the month will be assigned to the missing day
- If either the year is after the year of the end of study date or if both years are the same but the month is after the end of study date, then the stop date will be imputed as the end of study date.

9.2.2 Missing Severity Assessment for Adverse Events

If severity is missing for an AE, a severity of “Severe” will be assigned. The imputed values for severity assessment will be used for incidence summaries, while the actual values will be used in data listings.

9.2.3 Missing Relationship for Adverse Events

If the relationship to investigational product (as administered in Study OHB-607-202) is missing for an AE, a causality of “Related” will be assigned. If the relationship to study procedure performed in this study (SHP607-203) is missing for an AE starting on or after the date of informed consent, a causality of “Related” will be assigned. The imputed values for relationship will be used for incidence summaries, while the actual values will be presented in data listings.

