5. STUDY SUBJECTS

5.1 Disposition of Subjects

This section describes subject disposition for both the analysis sets and the study status.

The number of subjects included in each defined analysis set will be summarized by the antecedent treatment group as administered in Study OHB-607-202 (Standard Neonatal Care, SHP607 250 µg/kg/24 hours, and SHP607 400 µg/kg/24 hours) and overall.

Percentages will be provided using the Enrolled Set as the denominator.

The number and percentage of subjects who completed through the study visits (12-month, 18-month, 24-month, 30-month, 3-year, 3.5-year, 4-year, and 4.5-year CA), who completed the study, and who prematurely discontinued from the study will be presented for each treatment group and overall for the Enrolled Set. Primary reasons for premature discontinuation as recorded on the Study Completion page of the electronic case report

form (eCRF) will be summarized (number and percentage) by treatment group and overall. All subjects who prematurely discontinued will be listed for the Enrolled Set.

A by-subject listing of study completion information, including the reason for premature study discontinuation, where applicable, will be presented.

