7. SAFETY ANALYSIS

The safety analysis will be performed using the Safety Set. All safety analyses will be conducted according to the treatment the subject actually received in Study OHB-607-202.

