7.1 Adverse Events

Adverse events will be coded using Medical Dictionary for Regulatory Activities (MedDRA) Version 24.0 or newer. For the purposes of this study only the following adverse events will be presented:

- Specified targeted medical events (Protocol Section 8.1.4)
- AEs related to investigational product (as administered in Study OHB-607-202)
- AEs leading to withdrawal from the study
- Serious AEs that occur during the study period or were previously present and worsen during the study period.

If it is determined that any of the following targeted medical events have been experienced by a subject, they will be recorded as AEs or SAEs, as appropriate, regardless of relationship to prior investigational product (as administered in Study OHB-607-202). The targeted medical events are considered as AEs of important potential risks and identified based on a list of pre-specified preferred terms (PTs):

- Intracranial hypertension: intracranial pressure increased, benign intracranial hypertension, fontanelle bulging, delayed fontanelle closure
- Any abnormality of glucose metabolism: hypoglycaemia, hypoglycaemia neonatal, blood glucose decreased
- Tonsillar hypertrophy (based on tonsil examination [part of the physical examination]): tonsillar hypertrophy, adenoidal hypertrophy, thymus enlargement, hypoacusis, snoring, ear tube insertion, tonsillectomy, adenoidectomy, sleep apnoea syndrome
- Increased cardiac size: cardiomegaly, cardiac hypertrophy, cardiac septal hypertrophy, ventricular hypertrophy, atrial hypertrophy, left ventricular hypertrophy, right ventricular hypertrophy, left atrial hypertrophy, right atrial hypertrophy, cardiomyopathy, cardiomyopathy neonatal, hypertrophic cardiomyopathy

An overall summary of the number of subjects as well as the number of events in each treatment group and overall will be presented, including the number and percentage of subjects with:

- Any AE (as specified in Protocol Section 8.1)
- Any SAE
- Any severe AE
- Any AE related to investigational product (IP) as administered in Study OHB-607-202

- Any SAE related to IP as administered in Study OHB-607-202
- Any severe AE related to IP as administered in Study OHB-607-202
- Any AE related to procedures performed in this study (SHP607-203)
- Any SAE related to procedures performed in this study (SHP607-203)
- Any severe AE related to procedures performed in this study (SHP607-203)
- Any AE leading to study discontinuation
- Any SAE leading to death

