The number and percentage of subjects reporting AEs, as well as the number of events (except for tables by the maximum severity), in each treatment group and overall will be tabulated, respectively, in following ways:

- By system organ class (SOC) and PT for all AEs
- By the maximum severity, SOC and PT for all AEs
- By SOC and PT for all AEs considered related to IP as administered in Study OHB-607-202
- By SOC and PT for all AEs considered related to study procedures
- By SOC and PT for all AEs leading to death
- By SOC and PT for all AEs leading to study discontinuation
- By SOC and PT for all SAEs
- By risk term, seriousness, and relationship to antecedent IP for AEs of important potential risks
- Most frequent AEs by PT (sorted by frequency, occurring in $\geq 5\%$ of subjects in any treatment arm)

In tables by severity or relationship, missing severity or missing relationship imputation will be applied, and handling of those missing cases are detailed in Section [9.2.2](#) and [9.2.3](#), respectively. If a subject had multiple occurrences of the same AEs, the subject will be counted only once per SOC and once per PT at the maximum severity. Handling of incomplete AE start/end dates is described in Section [9.2.1](#).

All AEs will be presented in a data listing. Separate data listings will be presented for AEs related to the antecedent IP, AEs related to study procedures, AEs leading to death, SAEs and AEs of important potential risks.

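### The rule that turns a missing relationship to investigational product into 'Related' also covers standard-care children, who never received SHP607

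*SAP*

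**What the plan says.** SAP 9.2.3 has two imputation rules for AE relationship.

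- **Relationship to investigational product (IP).** "If the relationship to investigational product (as administered in Study OHB-607-202) is missing for an AE, a causality of" *Related* is assigned. The rule applies to any AE in any antecedent group.
- **Relationship to study procedures.** *Related* is assigned only where the field "is missing for an AE starting on or after the date of informed consent".

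The section then says where the results go: "The imputed values for relationship will be used for incidence summaries". The listings keep the actual values. SAP 7.1 repeats that the imputation is applied in tables by relationship and names no exception.

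On grouping, SAP 5.1 has subjects "summarized by the antecedent treatment group as administered in Study OHB-607-202 (Standard Neonatal Care" and the two SHP607 dose groups), plus overall. SAP Section 7 adds: "All safety analyses will be conducted according to the treatment the subject actually received in Study OHB-607-202". Protocol 1.3 describes the control arm of the antecedent study as standard neonatal care without study drug, and SAP 3.1 confirms that no IP is given in the present study.

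**The concern.** Imputing a missing causality as *Related* is a conventional conservative choice for a child who was exposed. For a child who never received the product it produces an impossible classification, and it is not conservative. It can only raise the comparator's count and so narrow the apparent difference between SHP607 and standard care. SAP 2.1 states the safety objective as a comparison with the standard care group.

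SAP Section 6 drops all efficacy analysis and SAP 3.1 limits reporting to designated safety data. The AE tables are therefore the main output of this terminated study. The groups are small, so a single artefact gives a noticeable percentage. A reader might discount a drug-related event in the control column, but the inflated overall column gives no such warning.

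**Working it through.** The plan states no figure to reproduce. The check is a comparison of texts, followed by arithmetic for scale.

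**Step 1. Is there an exposure condition anywhere?** The parenthesis in the IP rule identifies which product is meant; it does not restrict the rule to children who received it. SAP 5.1, 7, 7.1 and 9.2.3 contain no exemption for standard care. Grouping by treatment actually received makes the result more clearly impossible: a control infant who had in fact been given SHP607 would not be in the standard care column.

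**Step 2. Which outputs are affected?** SAP 7.1 presents these by treatment group and overall:

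1. Overview line for any IP-related AE.
2. Overview line: "Any SAE related to IP as administered in Study OHB-607-202".
3. Overview line for any severe IP-related AE.
4. Table: "By SOC and PT for all AEs considered related to IP as administered in Study OHB-607-202".
5. Table: "By risk term, seriousness, and relationship to antecedent IP for AEs of important potential risks".

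SAP 9.2.2 sets a missing severity to *Severe*, so an event with both fields blank would also enter output 3. SAP 7.1 plans a separate listing of AEs related to antecedent IP. Listings keep actual values, so that listing would disagree with the tables.

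**Step 3. Which events can be affected?** Protocol 8.1 collects targeted medical events, IP-related AEs, AEs leading to withdrawal, and SAEs. An AE collected only because it was judged IP-related already has its assessment, so the other three kinds are the ones at risk.

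**Step 4. Size for one standard-care child with a blank field.** Inputs: about 477 planned and fewer than 10% of that enrolled (SAP 3.1); 1:1:1 randomisation in the antecedent study (Protocol 1.3). An even split among those enrolled here is an assumption, as are the totals of 30 and 15.

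Maximum enrolled: 0.10 × 477 = 47.7, so at most 47. Per arm: 47/3 = 15.7, about 16. The effect of one child is 1/n.

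| Enrolled | Control arm | Shown in control column | Shown overall |
|---|---|---|---|
| 47 (upper limit) | 16 | 1/16 = 6.3% | 1/47 = 2.1% |
| 30 (assumed) | 10 | 1/10 = 10.0% | 1/30 = 3.3% |
| 15 (assumed) | 5 | 1/5 = 20.0% | 1/15 = 6.7% |

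The safety tables use the Safety Set, which cannot be larger than the Enrolled Set. For a given split, these percentages are therefore lower limits for one child.

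**Step 5. How likely is at least one blank?** With k control AEs, each independently blank with probability q, the chance is 1 − (1 − q)^k. Both k and q are assumed.

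| k | q = 0.01 | q = 0.05 |
|---|---|---|
| 5 | 4.9% | 22.6% |
| 10 | 9.6% | 40.1% |
| 20 | 18.2% | 64.2% |

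The documents do not say where in this range the study lies.

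**The case against.** The strongest reply is that the case should hardly ever arise. Protocol 8.1.2 requires the investigator to assess relationship for every AE and says to choose *not related* when there is no valid reason to suspect the product, which is plainly so for an unexposed child. The antecedent study is open-label, and Protocol 7.1 blinds only selected assessors, so the investigator can know that the child was a control. Protocol 9.2 has omissions queried. The eCRF may not accept a blank, and the table specifications, which SAP Section 1 places in a separate document, may show these rows as not applicable for standard care. Any artefact would be conspicuous and could be traced through the listings.

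This stands as an argument about frequency and weight. It does not repair the rule, which exists precisely for the blanks that survive these controls and should give a possible answer when it is used. What the eCRF or the table specifications contain cannot be assumed either way.

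Two further points have some force. A blank for an unexposed child could be read as not applicable rather than missing, but the SAP does not say so and the literal reading is the stronger one. The contrast with the procedure rule should not be pressed far: Protocol 8.1 collects AEs only from consent onwards, so that rule's date condition excludes little. It does show that a condition could easily be written into this section.

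**Conclusion.** The concern holds, as a minor point. As written, SAP 9.2.3 directs that a missing relationship for a standard-care child be tabulated as related to a product the child never received. That the text has this gap is certain. That a wrong count will appear is conditional on at least one blank field among control AEs, which is probably rare and cannot be quantified from the documents.

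If it happens, one child moves the control column from 0% to about 6.3% at the maximum enrolment, and further in a smaller study, on the even-split assumption. The consequence is confined to descriptive counts and percentages in the five outputs listed. No hypothesis test is affected, and the SHP607 columns do not change.

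**What to change.** Replace the first sentence of SAP 9.2.3 with wording to this effect: where an AE has no recorded relationship to IP, assign *Related* if the child actually received SHP607 (OHB-607) in Study OHB-607-202, and *Not related* if the child received standard neonatal care only.

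Apply this to missing values only. Recorded investigator assessments, the listings and the SAP 9.1 denominators, including the overall column, stay as they are. A recorded *Related* for a control child would therefore still be tabulated; that is a matter for data query, not imputation.

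The cost is one sentence and one programming condition on the treatment-received flag that SAP Section 7 already requires. The conservative imputation is kept in both SHP607 groups.

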9.3 ANALYSIS SOFTWARE

Statistical analyses will be performed using Version 9.4 (or newer) of SAS® on a suitably qualified environment.

10. CHANGES TO ANALYSIS SPECIFIED IN PROTOCOL

Protocol planned efficacy endpoints are not listed or analyzed in this abbreviated SAP due to early termination of the study.

